FAST in hemodynamically unstable trauma patients. We plan to prospectively collect data for creation of a multicenter database; enrolled subjects would undergo both the standard FAST and when appropriate (see Methods) a FASTeR. Our aim is to determine the sensitivity and specificity of the FAST and FASTeR, and determine which exam was more accurate in recognizing hemoperitoneum. Exam results will be confirmed with computed tomography (CT) imaging or operative findings.

Potential Risks and Benefits

Potential Risks

There are no expected medical risks to the study participants in excess of the normal risks of the FAST, which is minimal.

Potential Benefits

If the FASTeR is shown to detect small volumes of hemoperitoneum earlier than was previously possible with the FAST, patients may directly benefit from earlier diagnosis and treatment. Early identification of hemoperitoneum has been shown to be strongly correlated with increased survival rates (1).

Study Objectives

Primary Objective

To calculate and compare the sensitivity and specificity of detecting hemoperitoneum in the RUQ for the standard FAST and the FASTeR in the research subjects. Actual injury complex will be confirmed by CT or operative findings.

Secondary Objective

To calculate and compare the false positive rate, false negative rate, positive predictive value, negative predictive value, and positive and negative likelihood ratios for the standard FAST and FASTeR. Exam results for individual subjects will be compared to see if there is a significant difference in result accuracy.

Study Design

This is a prospective multicenter study. Detailed responsibilities for the lead (Memorial Regional Hospital) and satellite centers below.

Memorial Regional Hospital (lead)

- 1. Maintain database for enrolled MRH subjects. Data collected will include HIPAA identifiers (included in outcome measures) to monitor our own data integrity.
- 2. As lead center, MRH will aggregate and analyze collected data from satellite centers which will be submitted without HIPAA identifiers.
- 3. MRH to manage subjects meeting inclusion criteria according to our institutional patient management protocols.
- 4. MRH to adhere to IRB protocol and application as submitted.

Satellite Centers

- 1. Each center must apply and receive IRB approval from their respective IRB(s).
- 2. Each center is responsible for their own data integrity, as outlined in their approved IRB protocol and application.

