- 3. Each center to provide IRB outcome or waiver letter to the lead center.
- 4. Each center to complete the data sharing agreement specific to this study.
- 5. Each center to provide care according to their institutional patient management protocols.
- 6. Each center to submit de-identified data to the lead center for analysis.

Subject Selection

Inclusion Criteria

1. Patients over 18 and under 89 years of age who present as a trauma activation with clinical history or physical signs of blunt abdominal trauma and hemodynamic instability

Exclusion Criteria

- 1. Patients under 18 and over 89 years
- 2. Pregnant women
- 3. Patients with prohibitive right sided chest trauma
- 4. Patients in extremis undergoing salvage maneuvers (chest compressions or emergent surgical intervention) which prevents performance of an ultrasound examination
- 5. Patients who leave against medical advice or are otherwise removed from the medical system before their work up has been completed

Sample Size

50 participants at MRH and 250 participants total for all sites.

Research Design

This is a prospective multicenter study, where MRH will act as the lead center. Each contributing center is responsible for obtaining IRB approval and maintaining data integrity outlined in their approved IRB protocol and application from their respective institutions. Once IRB approval has been obtained, we will begin enrolling trauma patients prospectively into a registry. The participating centers for this study represent a diverse set of trauma centers and emergency departments and include institutions with varying trauma verifications (e.g. ACS and State), sizes, geographical/metropolitan locations, and resource availability to ensure inclusivity.

Since this is a prospective observational study, data will be collected prospectively without altering the manner in which the patients are managed by the surgeon and institution. Accordingly, an informed consent waiver is requested. Patients will be given a flyer with information about the study (see additional documents). Data will be collected for a two year period with interim analysis when specific enrollment targets are met. All data will be recorded on a data sheet and transferred to a secured database (REDCap) without patient identifiers.

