Patients with clinical history or physical signs suspicious for blunt abdominal trauma will undergo the standard FAST in the emergency department as per ATLS protocol. During the secondary survey, all patients are rolled for examination of their back and removal of the rigid spine board, per ATLS. In our study, we will standardize this practice so that all patients are rolled onto their right side for this portion of the examination. Patients with extensive right sided chest trauma will be excluded at the discretion of the Trauma Surgeon. After the right sided roll to remove the back board, a repeat ultrasound examination of the RUQ will be performed.

All participating centers, including MRH, will collect and submit the following data to the database for each enrolled subject: age, gender, initial trauma bay vital signs, mechanism of injury, results of the FAST, results of the FASTeR, and injury complex as confirmed by CT imaging or operative findings for their respective centers. Both the CT scan and any surgical intervention that the participant undergoes as a study subject will be performed through routine standard of care procedures. The database will not contain HIPAA identifiers

MRH will record our internal subject medical record numbers and dates of admission to verify data fields and monitor our own data integrity. All data will be de-identified prior to publication.

Study Outcome Measures (Endpoints)

The study outcome measures will be recorded using the "Multicenter Study: Can we be FASTeR? A multicenter study utilizing Right sided roll to improve sensitivity of the FAST examination" data collection form. The patient medical record number (MRN) will be

recorded by hand on the tool for all MRH enrolled subjects only; subject data will be cross-checked with the electronic records in order to maximize data integrity.

- 1. Number of patients admitted and discharged from MRH between the timeframe (October 16, 2017- October 16, 2019) who present as a trauma activation with clinical history or physical signs of blunt abdominal trauma and hemodynamic instability
 - a. MRN (recorded by hand), internal use only
 - b. Admission date (recorded by hand), internal use only
- 2. Demographics (e.g. age, gender)
- 3. Admission vital signs (e.g. heart rate [bpm], blood pressure, respiratory rate, oxygen saturation)
- 4. Results (positive or negative) of the FAST (RUQ, LUQ, surprapubic)
- 5. Results of the FASTeR (RUQ)

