We anticipate a rolling accruement of subjects over a two year period. A sample size calculation (power analysis) was performed to estimate the needed total participant accruement to provide a power of 90% and an alpha of <0.05. Standard FAST should identify up to 60% of subjects with significant intra-abdominal injury. If we assume that the FASTeR will identify hemoperitoneum in 1 of 4 subjects with intra-abdominal injury and previous negative FAST examination, then our needed sample size is 209 subjects. To account for subjects meeting exclusion criteria, we will plan to accrue 250 patients. Given that this sample size calculation was based on estimation regarding the sensitivity of the FASTeR in this patient population, interim analyses regarding primary endpoint will be conducted after 100 subjects have been accrued and again after 200 subjects have been accrued. Subject charts will be reviewed in increments of ten as they are enrolled.

Withdrawal of Subjects

Subjects that are unable to tolerate the position changes described in the protocol will be considered screening failures and will be automatically withdrawn from the study.

Subjects that receive the FASTeR are free to withdraw themselves from the study at any time. They may withdraw from the study by notifying the PI, [name], directly by phone. The option to withdraw and the contact information for [name] are listed on the study information flyer that will given to all subjects.

Quality Control and Quality Assurance

Study data will be collected and managed using REDCap electronic data capture tools. REDCap (Research Electronic Data Capture) is a secure, web-based application designed to support data capture for research studies, providing 1) an intuitive interface for validated data entry; 2) audit trails for tracking data manipulation and export procedures; 3) automated export procedures for seamless data downloads to common statistical packages; and 4) procedures for importing data from external sources (7).

Satellite centers are responsible for getting IRB approval and maintaining their own data integrity as outlined in their respective IRB protocols and applications. The lead center (MRH) will aggregate and analyze deindentified data collected in REDCap.

Ethical Considerations

This study is to be conducted according to US and international standards of Good Clinical Practice, applicable government regulations and Institutional research policies and procedures.

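### Subjects who cannot complete the right roll are withdrawn as screening failures, so FASTeR non-completion goes uncounted and accuracy is estimated only in those who complete it

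*Combined protocol and SAP*

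**What the plan says.** - **Withdrawal of Subjects** gives the rule: "Subjects that are unable to tolerate the position changes described in the protocol will be considered screening failures and will be automatically withdrawn from the" trial. The section does not say whether the inability is judged before or during the roll.
- **Exclusion Criteria:** there are five, and intolerance of the roll is not among them. The nearest is "Patients with prohibitive right sided chest trauma", which Research Design leaves to the trauma surgeon's discretion.
- **Research Design:** the standard FAST comes first, then the roll, then the repeat RUQ scan. Rolling is described as routine: "all patients are rolled for examination of their back and removal of the rigid spine board, per ATLS". The study fixes the side: "In our study, we will standardize this practice so that all patients are rolled onto their right side for this portion of the examination".
- **Study Outcome Measures:** eight items are listed. They cover eligibility, demographics, admission vital signs, FAST and FASTeR results, the method and content of the final injury complex, and confirmed hemoperitoneum. None records whether the roll was completed, or why not, and no vital sign after the roll is collected.
- **Statistical Analysis Plan:** the analysis set is subjects who meet the inclusion criteria and have complete data.
- **Study Duration:** accrual is raised from 209 to 250 to allow for subjects who meet exclusion criteria. Intolerance is not named.

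**The concern.** The Rationale proposes a change of practice: roll to the right and rescan. The population is hemodynamically unstable, and the plan itself foresees that some subjects will not manage the position. Anyone deciding whether to adopt FASTeR needs two numbers: how accurate it is when done, and how often it cannot be done. The plan is set up to give only the first.

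The withdrawal rule also selects the analysis set. In a paired comparison of two tests, a subject who had the first test but could not complete the second is a failed index test, and a listed exclusion is something different. Removing such subjects restricts sensitivity, specificity and McNemar's test to people in whom FASTeR worked logistically. The result may then be read as applying to everyone for whom FASTeR is intended.

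**Working it through.** **1. Follow one subject through the plan.** An eligible subject has the standard FAST, the roll is started, and the position is not tolerated. No listed exclusion applies. Under Withdrawal of Subjects this person nevertheless becomes a screening failure and is withdrawn. The form has a place for the FASTeR result but none for a failed attempt. Even without the withdrawal rule, the missing FASTeR result would remove the subject under the complete-data rule. So two separate rules take the subject out of the analysis, and no planned table counts the subject.

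**2. What the sample size section assumes.** FAST sensitivity is up to 60%. FASTeR is assumed to find hemoperitoneum in 1 of 4 injured subjects missed by FAST. The gain is 0.25 × (1 − 0.60) = 0.10, so FASTeR sensitivity is 0.60 + 0.10 = 70%, a difference of 10 points.

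**3. Illustration in all intended subjects.** Let *f* be the proportion who cannot complete the roll. The documents give no value, so 5% to 20% is assumed. Also assumed: the same *f* applies in subjects with hemoperitoneum, and FAST sensitivity is 60% in non-completers as well.

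- FAST result stands in for the missing FASTeR: (1 − *f*) × 0.70 + *f* × 0.60
- Missing FASTeR counted as missed: (1 − *f*) × 0.70

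| *f* (assumed) | FAST stands | Gain over 60% | Counted as missed | Gain over 60% |
|---|---|---|---|---|
| 5% | 0.665 + 0.030 = 69.5% | +9.5 points | 66.5% | +6.5 points |
| 10% | 0.630 + 0.060 = 69.0% | +9.0 points | 63.0% | +3.0 points |
| 20% | 0.560 + 0.120 = 68.0% | +8.0 points | 56.0% | −4.0 points |

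Under the second rule the assumed gain disappears when (1 − *f*) × 0.70 = 0.60, that is at *f* = 1/7, or about 14%.

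**4. Effect on McNemar's test.** If the FAST result stands in, each non-completer is a concordant pair and adds nothing to the test statistic; only the estimated difference is diluted. If the missing FASTeR counts as incorrect, every non-completer whose FAST was correct becomes a discordant pair against FASTeR. The two rules therefore show how far the comparison depends on the treatment of these subjects.

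**The case against.** The strongest reply is that rolling is ordinary trauma care. Research Design says all patients are rolled anyway, so the study adds only the side and a second look at the RUQ. The objectives are about diagnostic accuracy, and accuracy among those who have the test is a legitimate target. The rule may also cover subjects judged unable before any roll, for whom screening failure is a more natural label. Nothing forbids reporting the number of screening failures.

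Much of this stands, and it limits what can be claimed. Four stronger readings are tempting, and the documents do not support them:

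- **A reader might infer that a safety event is being removed from the results.** The documents never call intolerance a safety event and plan no safety result. The Potential Risks section says "There are no expected medical risks to the study participants in excess of the normal risks of the FAST, which is minimal", which is consistent with treating the roll as routine, so the point does not call for a change there.
- **A reader might infer that intolerance can only appear once the roll has begun.** The timing is not stated. It may appear then, which is enough for the point.
- **A reader might infer that nobody overseeing the study could notice a problem.** Charts are reviewed in tens, and the lead center's data are checked against electronic records. A stopped roll might be found there, although no field captures it.
- **A reader might infer that the study will in effect report no intolerance among about 209 subjects.** The plan reports no tolerance rate, and silence is not a zero. Nor does 209 follow: it would take 250 − 209 = 41 losses, and that reserve is assigned to exclusion criteria.

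The core is untouched. Routine rolling does not make completion of FASTeR known, and a count that is permitted but neither recorded nor required cannot be relied on.

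**Conclusion.** The point holds as one of recording and analysis. The withdrawal rule, the missing form item and the complete-data rule together leave FASTeR non-completion without any planned count. They confine the accuracy estimates to subjects who complete the roll.

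The size cannot be determined from the documents. Within the assumed range the effect is small if the standard FAST result is taken to stand (at most 2 points of sensitivity). It can exceed the whole assumed 10-point gain if non-completion counts as a miss. Both results rest on the assumed intolerance rates, on equal intolerance in subjects with and without hemoperitoneum, and on 60% FAST sensitivity in non-completers. The change is inexpensive and should be made.

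**What to change.** 1. **Replace the sentence in Withdrawal of Subjects**, for example: 'Eligible subjects who had the standard FAST but did not complete the right roll remain in the database. FASTeR is recorded as not completed, with the reason. The term screening failure is kept for subjects who meet a listed exclusion criterion before the roll.'
2. **Add one form field:** roll completed / not tolerated / stopped / not attempted. The last option separates inability judged beforehand from inability seen during the roll.
3. **Report the proportion not completed**, with an exact confidence interval, among all eligible subjects who had a FAST.
4. **Add a sensitivity analysis** of sensitivity, specificity and McNemar's test in all these subjects, once with the FAST result standing in for the missing FASTeR and once counting it as incorrect. State that 'FASTeR not completed' does not make a record incomplete for this analysis. The completers-only analysis can stay beside it, labelled as such.

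The cost is one sentence, one field and one table, plus the possibility that a non-zero failure rate appears in the report. The change concerns recording and analysis only; decisions about rolling, or stopping a roll, stay where they are.
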